8.1.2 Treatment Period

Treatment Period assessments are listed in [Table 3-2](#).

The Treatment Period will be conducted as described previously in Section 8.1. Dosing details are given in Section 10.2.

Subjects who prematurely discontinue study drug treatment will remain in the study from the time of discontinuation through the Safety Follow-up Visit, as described in Section 8.1.4.

8.1.3 Follow-up

Subjects will have a Safety Follow-up Visit 4 weeks (± 7 days) after the last study drug dose. Safety Follow-up Visit assessments are listed in [Table 3-2](#). When the Safety Follow-up Visit is complete, the subject has completed the study.

8.1.4 Early Termination of Treatment

If the subject prematurely discontinues study drug, an Early Termination of Treatment (ETT) Visit will be scheduled as soon as possible after the subject decides to terminate study drug. Subjects who prematurely discontinue study drug will also complete the Safety Follow-up Visit, approximately 4 weeks ± 7 days after their last dose of study drug. The assessments performed at the Safety Follow-up Visit are listed in [Table 3-2](#).

If the ETT Visit occurs 3 weeks after the last dose of study drug or later, then the ETT Visit will replace the Safety Follow-up Visit, and a separate Safety Follow-up Visit will not be required.

If the subject withdraws consent for the study, no further evaluations will be performed, and no additional data will be collected. Vertex Pharmaceuticals Incorporated (Vertex) may retain and continue to use any data collected before such withdrawal of consent.

8.2 Rationale for Study Design and Study Drug Regimens

8.2.1 Study Design

This study is designed to evaluate the effect of LUM/IVA therapy on exercise tolerance in subjects with CF after up to 24 weeks of LUM/IVA therapy. CPETs will be used to assess improvements in exercise tolerance, as measured by VO_{2max} .

The use of a placebo control group is deemed necessary because exercise tolerance can be affected by a number of factors, including activity level, and subject activity may increase as a result of being involved in an exercise tolerance study.

This study will only enroll subjects who have not previously been exposed to LUM or IVA, and all subjects will continue their normal, stable treatment for CF throughout the study.

The study population will be subjects with CF who are 12 years of age and older and are homozygous for the *F508del-CFTR* mutation. Efficacy, safety, and pharmacokinetic profiles for LUM/IVA therapy were established in subjects 12 years of age and older with CF homozygous for the *F508del-CFTR* mutation in Studies VX12-809-103 (Study 103) and

VX12-809-104 (Study 104). Furthermore, this is the population for which LUM/IVA treatment has been approved in Europe and in the US.

8.2.2 Study Drug Dose and Duration

The dosing regimen for LUM/IVA (LUM 400 mg/IVA 250 mg every 12 hours [q12h]) was selected on the basis of acceptable tolerability and favorable exposure observed in previous clinical studies of LUM/IVA,²⁹ and because it has been approved in Europe and in the US for the treatment of CF in patients age 12 years and older who are homozygous for the *F508del* mutation.^{30,31}

8.2.3 Rationale for Study Assessments

CPET: Maximal cardiopulmonary exercise testing that incorporates measurements of gas exchange provides precise measurements of exercise tolerance. This assessment provides several parameters of exercise tolerance and aerobic fitness including VO_2 , functional VO_2 gain, VCO_2 , AT, and VE. Functional VO_2 gain relates oxygen uptake to total ventilation during exercise and is an index of cardiopulmonary reserve. The VE versus VCO_2 slope is a measure of ventilatory efficiency. The AT is the exercise intensity at which lactate starts to accumulate.

Spirometry: Because lung disease is the major cause of morbidity and mortality for patients with CF, FEV₁, as measured by spirometry, is the most widely implemented standardized assessment to evaluate lung function in CF.

Actigraphy: Exercise tolerance can be affected by a number of factors, including activity level. In this study, subjects' activity levels will be monitored by actigraphy to determine whether subjects' activity increased with LUM/IVA treatment and to examine the relationship between physical activity and changes in exercise tolerance. Actigraphy will also be used to capture sleep/wake data, which reflect both functional and physiological health of subjects. The actigraph device can capture continuous sleep/wake data over a long period of time, is a cost-effective and minimally invasive in-home alternative to other methods to measure these behaviors (e.g., polysomnography), and offers a level of accuracy and reliability that cannot be achieved through subjective reports.

BMI: Malnutrition is common in patients with CF because of increased energy expenditures due to lung disease and fat malabsorption. Improved nutritional status, defined as an increase in weight and/or BMI, is an endpoint that has been used in previous clinical studies of LUM/IVA therapy (Studies 103 and 104).

Questionnaires pertaining to quality of life, depression, and anxiety—the CFQ-R, PHQ-R, and GAD-7: The CFQ-R is a validated CF-specific instrument that measures the health-related quality of life of patients with CF.^{32,33,34} The adolescent/adult version, the parent/caregiver version, and the child version measure quality-of-life domains including respiratory symptoms, digestive symptoms, emotion, and health perception. Furthermore, the CFQ-R has been evaluated in clinical studies involving therapies for CF lung disease.^{35,36,37} Linguistically validated versions of the CFQ-R^{38,39} are available, thereby allowing consistent interpretation of the results in this global study.

Several recent studies have documented the high rates of symptoms of depression and anxiety in patients with CF.⁴⁰⁻⁴³ The PHQ-8 is used to assess the presence of depressive symptoms in non-depression studies via 8 items that correspond to diagnostic criteria for major depressive disorder and depression severity. Various levels in the resulting score correspond to various levels of depression severity. The GAD-7 assesses the presence of anxiety symptoms via 7 items that are based on the symptom criteria for generalized anxiety disorder

9 STUDY POPULATION

Eligibility will be reviewed and documented by an appropriately qualified member of the investigator's team before subjects are enrolled.

9.1 Inclusion Criteria

Subjects who meet all of the following inclusion criteria will be eligible:

1. Subject (or their legally appointed and authorized representative) will sign and date an informed consent form (ICF), and where appropriate, assent form.
2. Willing and able to comply with scheduled visits, treatment plan, study restrictions, laboratory tests, contraceptive guidelines, and other study procedures.
3. Subjects (male and female) will be at least 12 years old on the date of informed consent.
4. Homozygous for the *F508del-CFTR* mutation (as documented in the subject's medical records or from genotyping performed during screening).

5. Confirmed diagnosis of CF⁴⁴ defined as a sweat chloride value ≥ 60 mmol/L by quantitative pilocarpine iontophoresis, as documented:
 - in the subject's medical records **OR**
 - from sweat chloride test result obtained during screening (to be conducted only if the subject does not have a sweat chloride test result in the medical records).
6. Stable CF disease as judged by the investigator.
7. FEV₁ at least 40% and not greater than 90% of predicted.
8. Willing to remain on a stable CF medication regimen through the Safety Follow-up Visit.

9.2 Exclusion Criteria

Subjects who meet any of the following exclusion criteria will **not** be eligible:

1. History of any comorbidity that might confound the results of the study, interfere with the use of CPET as an assessment, or pose an additional risk in administering study drug to the subject. For example:
 - history of cirrhosis with portal hypertension.
 - inability to exercise.
 - requiring additional oxygen with exercise.
2. Any of the following abnormal laboratory values at Screening:
 - hemoglobin < 10 g/dL.
 - any 2 or more of the following: aspartate aminotransferase (AST) $\geq 3 \times$ upper limit of normal (ULN), alanine aminotransferase (ALT) $\geq 3 \times$ ULN, gamma-glutamyl transpeptidase (GGT) $\geq 3 \times$ ULN, or alkaline phosphatase (ALP) $\geq 3 \times$ ULN.
 - total bilirubin $\geq 2 \times$ ULN.
 - AST or ALT $\geq 5 \times$ ULN.
 - glomerular filtration rate ≤ 50 mL/min/1.73 m² (calculated by the Modification of Diet in Renal Disease Study Equation)^{45,46} for subjects ≥ 18 years of age and ≤ 45 mL/min/1.73 m² (calculated by the Counahan-Barratt equation)⁴⁷ for subjects aged 12 to 17 years (inclusive).
3. An acute upper or lower respiratory infection, pulmonary exacerbation, or changes in therapy (including antibiotics) for pulmonary disease within 28 days before Day 1.
4. A 12-lead electrocardiogram (ECG) demonstrating QTc > 450 msec at Screening. If QTc exceeds 450 msec for the screening ECG, the ECG will be repeated 2 more times during the Screening Period, and the average of the 3 QTc values will be used to determine the subject's eligibility.

5. History of cardiac arrhythmia, ischemic heart disease, congestive heart failure, or other clinically significant cardiac condition, or medical condition requiring chronic use of a beta blocker, non-dihydropyridine calcium channel blocker, or other cardiac medication known to affect exercise tolerance.
6. History of solid organ or hematological transplantation.
7. For subjects under 18 years of age at Screening, except those who have had bilateral lens removal: history or evidence of cataract, lens opacity, Y-suture, or lamellar rings determined to be clinically significant by the ophthalmologist or optometrist during the ophthalmologic examination during the Screening Period. (The ophthalmologic examination does not need to be performed at Screening if there is documentation of an examination meeting protocol criteria that was conducted within 3 months before the Screening Visit.)
8. Using or expected to require any concomitant medication that is prohibited in this study, as discussed in Section 9.4.1.
9. History of alcohol or drug abuse, as deemed by the investigator, in the past year, including but not limited to cannabis, cocaine, and opiates.
10. Participation in an investigational drug study within 30 days before the Screening Visit.
11. Any previous exposure to LUM or IVA.
12. Pregnant or nursing females (females of childbearing potential must have a negative pregnancy test at Screening and Day 1); males with a female partner who is pregnant or nursing.
13. The subject or a close relative of the subject is the investigator or a subinvestigator, research assistant, pharmacist, study coordinator, or other staff directly involved with the conduct of the study. An adult (aged 18 years or older) who is a relative of a study staff member may be randomized in the study provided that
 - the adult lives independently of and does not reside with the study staff member.
 - the adult participates in the study at a site other than the site at which the family member is employed.
14. Colonization with organisms associated with a more rapid decline in pulmonary status (e.g., *Burkholderia cenocepacia*, *Burkholderia dolosa*, or *Mycobacterium abscessus*). For subjects who have had a history of a positive culture in the past, the investigator could be guided by the following suggested criteria for a subject to be considered free of colonization:
 - The subject should have had 2 respiratory tract cultures negative for these organisms within the past 12 months, with no subsequent positive cultures.
 - These 2 respiratory tract cultures should have been separated by at least 3 months.
 - One of these 2 respiratory tract cultures should have been obtained within the past 6 months.

9.3 Study Restrictions

Prohibited medications and certain foods are not allowed (Screening Period through Week 24) as summarized in Table 9-1.

A nonexhaustive list of study prohibitions and cautions for food and medication will be provided.

Table 9-1 Study Restrictions

Restricted Medication/Food ^a	Study Period	
	Screening Period	Treatment Period
Strong CYP3A inducers	None allowed within 14 days before the first dose of study drug	None allowed
Strong CYP3A inhibitors	None allowed within 14 days before the first dose of study drug	Use with caution

Note: The use of restricted medication in subjects with a medical need will be addressed on a case-by-case basis with the medical monitor or authorized designee.

^a See Section 9.4 for guidance for concomitant medications.

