8 STUDY DESIGN

8.1 Overview of Study Design

This is a Phase 4, randomized, double-blind, placebo-controlled, parallel-group study in subjects aged 12 years and older with CF who are homozygous for the *F508del-CFTR* mutation. This study is designed to evaluate the effect of LUM/IVA on exercise tolerance.

The study includes a Screening Period, a Treatment Period, and a Safety Follow-up Visit. Approximately 66 subjects will be randomized 1:1 (LUM/IVA:placebo) to the treatment arms shown in [Figure 8-1](#) and stratified by ppFEV₁ at baseline (<70% and ≥70% predicted). Subjects will receive study drug (LUM/IVA or placebo) for 24 weeks, in addition to their current CF medication regimen. They will return to the study center 4 weeks after their last dose of study drug for the Safety Follow-up Visit. It is recommended that subjects remain on a stable CF medication regimen from 4 weeks before Day 1 through the Safety Follow-up Visit.

Subjects will be reminded of the standard exercise recommendations for patients with CF, and their daily activity will be tracked using an actigraphy device.

[figure not shown]
[figure not shown]

Figure 8-1 Schematic View of the Study Design

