9.4 Prior and Concomitant Medications

9.4.1 Prohibited Medications

Prohibited medications as described in Table 9-1 are not allowed while subjects are receiving study drug.

The use of cytochrome P450 (CYP) 3A substrates is not prohibited, but investigators need to be aware that LUM appears to be a strong inducer of this CYP isoenzyme. Therefore, the efficacy of drugs extensively metabolized by this isoenzyme may be affected. Each investigator should evaluate the benefit/risk ratio of using such drugs with LUM during this study. Investigators should discuss any concerns regarding the use of CYP3A substrates during this study with the Vertex medical monitor or authorized designee.

The use of CYP2C and CYP2B6 substrates are not prohibited, but investigators need to be aware that LUM has been shown in vitro to induce CYP2B6, CYP2C8, CYP2C9, and CYP2C19; inhibition of CYP2C8 and CYP2C9 has also been observed in vitro. Additionally, in vitro studies suggest that IVA may inhibit CYP2C9. Therefore, concomitant use of LUM in combination with IVA with CYP2B6, CYP2C8, CYP2C9, and CYP2C19 substrates may alter the exposure of these substrates.

Each investigator should evaluate the benefit-risk ratio of using such drugs with LUM and IVA during this study and discuss the use of these substrates during this study with the medical monitor or authorized designee.

The use of strong inhibitors of CYP3A is not prohibited, but investigators need to be aware that a strong inhibitor of CYP3A has been shown to increase the exposure of IVA when given in combination with LUM; however, due to the induction effect of LUM, the net exposure of IVA is not expected to exceed previous experiences with IVA monotherapy. Subjects who are using strong CYP3A inhibitors do not require study drug interruption.

However, if they interrupt study drug for more than 72 hours, study drug resumption requires medical monitor discussion and approval. Each investigator should evaluate the benefit-risk ratio of using such drugs with LUM and IVA during this study and discuss the use of these strong inhibitors of CYP3A during this study with the medical monitor or authorized designee.

A nonexhaustive study prohibitions and cautions list for food and medications will be provided.

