9.4 Safety Analysis

The overall safety profile of study drug will be assessed in terms of the following safety and tolerability endpoints:

- Adverse events
- Clinical laboratory values (hematology, serum chemistry, urinalysis, and coagulation studies)

Safety endpoints will be analyzed based on the Safety Set. Only descriptive analysis of safety will be performed (i.e., no statistical testing will be performed).

The study period will be divided into 3 segments:

- The **pre-treatment period** is defined as the period after the informed consent/assent date and before the initial dosing of study drug.
- The **treatment-emergent period** is the period at or after the initial dosing (including day 1) of study drug to 28 days after the last dose of study drug.
- The **post-treatment period** is defined as the period after 28 days after last dose until the end of study.

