Appendix G Important Protocol Deviation Programming Rules (Based on the Clinical Database)

Important protocol deviations before first dose

1. Individual screening assessment(s) that did not meet eligibility criteria, excluding the exceptions that are permitted per protocol, were repeated
2. Screening visit performed outside of the -28 to -1 day window
3. Subject randomized and screening ophthalmologic examination greater than 3 months prior to Screening Visit
4. Height not collected for subjects who were 21 years of age or younger at the Screening Visit.

Important protocol deviations during treatment period

5. ETT visit was less than 3 weeks after the last dose of study drug but no Safety Follow-up Visit was performed.
6. After subject study completion/early discontinuation, prior study visits not done
7. Subject who prematurely discontinues study drug treatment did not complete the ETT visit
8. CPET not performed per protocol schedule
9. Prohibited medication taken during study
10. Initial dose of study drug not administered on Day 1.

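### Neither document's restriction, deviation or adverse-event rules name non-study LUM/IVA, so if a placebo subject starts the marketed product after stopping study drug, later events count as placebo TEAEs

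*Protocol*

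**What the plan says.** The trial compares LUM/IVA with placebo. Protocol 8.2.1 says of the subjects that "this is the population for which LUM/IVA treatment has been approved in Europe and in the US". Exclusion 11 rules out "Any previous exposure to LUM or IVA". After entry, the relevant rules are these:

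- **Protocol 9.3 and Table 9-1.** "Prohibited medications and certain foods are not allowed (Screening Period through Week 24) as summarized in Table 9-1". The table has two rows. "Strong CYP3A inducers" are not allowed in the Treatment Period, and strong CYP3A inhibitors are to be used with caution. A note leaves cases of medical need to individual discussion. A further, nonexhaustive list is promised but is not part of these documents.
- **Protocol 9.4.1.** The ban applies for as long as the subject is receiving study drug. On CYP3A, the section says that "LUM appears to be a strong inducer of this CYP isoenzyme".
- **Protocol 8.1.** "It is recommended that subjects remain on a stable CF medication regimen from 4 weeks before Day 1 through the Safety Follow-up Visit". Section 9.4.2 repeats the recommendation. Section 8.2.1 says without qualification that all subjects will keep to their stable treatment. Inclusion 8 asks for willingness to do so.
- **SAP 9.4.** The treatment-emergent period runs from the initial dosing "of study drug to 28 days after the last dose of study drug". SAP 9.4.1 instead ends the TEAE definition at the close of safety follow-up. SAP 8.2 analyses the Safety Set as treated.
- **SAP Appendix G, rule 9.** The important deviation is worded "Prohibited medication taken during study".

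**The concern.** Prior exposure to the test drug disqualifies a subject at entry, but no rule names exposure from outside the study afterwards. The drug can be prescribed to these subjects, and a subject who has finished or stopped blinded treatment has an evident reason to start it.

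If a placebo subject does so inside the adverse-event window, the test drug's early events are credited to placebo. Assuming that the drug raises event rates over placebo, the tabulated difference shrinks, so the error runs toward hiding a safety signal. Safety is only described in this trial, with no testing, so the by-arm TEAE tables are the result that readers will use.

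**Working it through.** The plan gives no figure on this point and no expected rate of uptake, so the check sets the rules side by side over time.

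**1. While the subject takes study drug.** Table 9-1 allows no strong CYP3A inducers in the Treatment Period. Section 9.4.1 says LUM appears to be one. Appendix G rule 9 makes prohibited medication an important deviation. Together these cover marketed LUM/IVA. The link is indirect: it works only if whoever codes the medication classes the test drug itself as a strong inducer. It does not reach IVA alone, which Section 9.4.1 does not describe as a CYP3A inducer.

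**2. After study drug stops.** The two protocol sections give different end points.
- Completer: Section 9.3 ends the restriction at Week 24 and Section 9.4.1 at the last dose, the evening before the Week 24 Visit. On either reading, no restriction applies during follow-up.
- Early discontinuer: Section 9.3 still restricts through Week 24, whereas Section 9.4.1 has already released the subject.
- Both: what remains is the stable-regimen recommendation.
- Rule 9 depends on the word prohibited, so it is not clearly triggered here. It also stands under a heading for the treatment period, although rule 5 under that heading concerns the Safety Follow-up Visit.

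**3. Length of the exposed window.** Inputs are 24 weeks of treatment (24 × 7 = 168 days) and the 28-day tail in SAP 9.4.
- Treatment-emergent days for a completer: 168 + 28 = 196.
- Share after the restriction ends: 28 / 196 = 14.3%.
- As an illustration, a subject who stops at Week 12 has 84 + 28 = 112 treatment-emergent days. On the Section 9.4.1 reading, 28 / 112 = 25% of them are unrestricted; on the Section 9.3 reading, none are.
- The Safety Follow-up Visit is allowed at 4 weeks ± 7 days, that is 21 to 35 days after last dose. Under SAP 9.4.1 the TEAE window can therefore reach day 35, while the same section calls events after day 28 post-treatment.

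These are shares of observation time. Turning them into bias would need a switching rate and event rates on and off the drug, and the documents give none of these.

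**4. How events in the window are assigned.** SAP 9.4 and 9.4.1 contain no cut-off and no separate display once non-study LUM/IVA starts. The as-treated rule in SAP 8.2 does not say what happens when the treatment was obtained outside the study. By default the event stays in the placebo column.

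**5. Route to the primary endpoint.** SAP 9.3 keeps measurements after discontinuation up to Week 24. In Table 3-2, however, a subject who stops has one further CPET, at the ETT Visit, to be held as soon as possible. The Safety Follow-up Visit has no CPET and ends participation. A completer has no CPET after Week 24. VO2max measured on marketed drug therefore requires either a late ETT Visit (the protocol allows for one 3 weeks or more after last dose) or use alongside blinded drug, which step 1 covers by inference.

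**The case against.** The strongest reply is that the plan already handles this. During treatment the inducer row and rule 9 apply. Important deviations can also come from the site deviation log (SAP 9.2.2), and Protocol 12.3.2.5 sets the identification rules at a blinded review before lock. All medications are recorded through the Safety Follow-up Visit (Protocol 9.4.2), summarized by treatment group (Protocol 12.3.2.3) and tabulated by preferred term (SAP 9.2.3). The separate list of prohibitions may name LUM/IVA.

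Most of this stands, and it defeats three stronger readings that a reader might infer:

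- *Use of the marketed product goes unflagged throughout.* Not so during study treatment, where it falls into a prohibited class.
- *No planned output would reveal it.* Not so. The concomitant-medication table would show it in the placebo column. What is missing is any link from the start date to later events.
- *The primary comparison loses power.* The documents give no uptake rate, and the CPET schedule leaves only the narrow routes in step 5, so no power figure is supportable.

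It can also be said that ending a TEAE window at a post-randomization event discards safety data. That is fair, and it is a reason to add a summary while keeping the standard table.

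None of this answers the follow-up window, where the restriction has lapsed or is disputed and events are still counted.

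**Conclusion.** The point holds for adverse events after study drug stops. Non-study LUM/IVA is covered only by inference on treatment, its status afterwards is unclear, and the SAP has no rule for events that follow its start. Such events in a placebo subject are tabulated as placebo TEAEs. The direction, toward no difference, rests on the assumption that the drug causes more events than placebo. The size cannot be stated: 28 of 196 days is the time at risk of misattribution for a completer, and the bias also depends on how many subjects switch and when. If nobody switches, nothing changes.

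Any efficacy effect is confined to late ETT tests or concurrent use and cannot be quantified from the documents. The sample size is not in question. The correction is worth making before data lock because it is cheap and the data are already collected.

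**What to change.** 1. **SAP Appendix G.** Add a flag, by drug name, for any non-study LUM or IVA from first dose through the Safety Follow-up Visit, and report the number of subjects by arm. The flag records use; it does not decide whether use is permitted.
2. **SAP 9.4.** Keep the standard TEAE table. Add a TEAE summary by arm that ends at the earlier of 28 days after last dose and first non-study LUM/IVA use, with later events listed separately. State how the as-treated rule applies to such subjects.
3. **Protocol.** Sections 8.1, 8.2.1, 9.3, 9.4.1 and 9.4.2 must be reconciled on what applies to non-study LUM/IVA and until when. No clinical rule is proposed here.

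The cost is SAP wording, one flag derived from existing concomitant-medication data, one extra table and a listing. The downside is slightly less event time for affected subjects in the added table; the standard table loses nothing.
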